3.7. Disordered Eating Attitudes

Eating behavior will be assessed with a standard Eating Attitudes Test-26 (EAT-26), a self-administrated questionnaire. The questionnaire consists of 26 questions related to attitudes and beliefs, behavior related to eating, the perception of appearance, and body weight.

The participant replies to a question by selecting one response: always, usually, often, sometimes, rarely, never. In the first 25 questions, the answer ‘always’ is worth 3 points, ‘usually’, 2 points, and ‘often’, 1 point. In question 26, the answer ‘never’ is worth 3 points, ‘rarely’, 2 points, and ‘sometimes’, 1 point. A total score of 20 or more points indicates DEA (Disordered Eating Attitudes).

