Study Protocol: Ovarian Hyperandrogenism in Adolescent Girls and Concomitant Metabolic Changes, Oxidative Stress, Inflammation, Oral Health and Their Relation to Diet

Poznan University of Physical Education
Dietetic Department
[name]
Principal Investigator: [name]
Phone: ([contact]

Poznan University of Medical Sciences
Department of Paediatric Dentistry
[name]
Principal Investigators: [name],
Phone: ([contact]
Department of Perinatology and Gynecology
Division of Developmental Gynecology and Sexology
Principal Investigator: [name]

STUDY PROTOCOL

Ovarian Hyperandrogenism in Adolescent Girls and Concomitant Metabolic Changes, Oxidative Stress, Inflammation, Oral Health and Their Relation to Diet

1. Introduction

Hyperandrogenism in women is a state of increased androgen production, manifested by irregular menstrual cycles, a more frequent incidence of infertility, metabolic syndrome, oxidative stress, and inflammation, as well as acne and hirsutism. In addition to ovulation disorders and the multifollicular ovaries structure in an ultrasound examination, hyperandrogenism is a typical clinical feature of the Polycystic Ovary Syndrome (PCOS), which is diagnosed in approximately 8.6% of adolescent girls. Excessive body weight makes it difficult to diagnose at an early stage of the disease and intensifies metabolic and hormonal disorders, as well as those related to oxidative stress and inflammation of the body. Some research studies suggest that PCOS may negatively affect oral health of women, increasing the risk of periodontal problems.

The main purpose of this research was to check whether serum androgen levels and concomitant metabolic changes, oxidative stress, inflammation and oral health in adolescent girls with hyperandrogenism may be related to diet.

The investigators aimed to identify the factors that increase the risk of being overweight and of obesity among adolescents with clinical features of PCOS, related to diet and DEA (Disordered Eating Attitudes).

The objective was also to investigate the relationships between markers of oxidation and markers of Systemic Inflammation and macronutrients intake, such as carbohydrates and fiber, protein (animal, plant), fats and cholesterol in normal and overweight/obese girls with clinical features of PCOS.

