Additionally, the investigators would like to evaluate the relation between oral health of girls with PCOS (including condition of periodontium and dental caries) and their dietary habits, hormonal, metabolic and oxidative and inflammatory status.

2. Characteristics of tested population

The research will be carried out with the participation of 200 Caucasian adolescent girls, patients at the Gynecology and Obstetrics Hospital of Poznan University of Medical Sciences and Department of Perinatology and Gynecology, Division of Developmental Gynecology and Sexology, Poznan University of Medical Sciences, aged 13–18 years

Inclusion Criteria:

- Gender: Female
- Minimum Age: 13 Years
- Maximum Age: 18 Years
- Written consent for inclusion (girls and their parents)
- clinical and/or biochemical hyperandrogenism (hirsutism with moderate to severe acne, and/or elevation of serum total testosterone or free testosterone,
- oligoovulation (based on oligomenorrhea defined as bleeding episodes occurring less than 8 times per year or secondary amenorrhea),
- polycystic ovarian picture in an ultrasound examination (at least 12 follicles in each ovary each measuring 2-9 mm in diameter and/or ovarian volume >10 mL).

Exclusion Criteria:

- any systemic disease, thyroid dysfunction, diabetes, congenital adrenal hyperplasia, Cushing syndrome, hyperprolactinemia suggestive of pituitary adenoma and androgen-secreting tumors
- medications of continuous use,
- the use of hormonal therapy or antibiotics in the past three months,
- vitamin or supplements use,
- alcohol consumption
- smoking

3. Methods

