3.1. Evaluation of anthropometric indices and body composition

3.1.1. Anthropometric Assessment

Body mass index BMI: derived from measured body height (m) and body weight (kg) as body weight / height². Weight will be measured to the nearest 0.1 kg using digital medical scales. Height will be measured with a stadiometer attached to the scales.

Diagnosis and classification of overweight and obesity will base on BMI, according to World Health Organisation (WHO) for children aged 5–19 years overweight and obesity correspond to BMI-for-age greater than 1 standard deviation and 2 standard deviations above the WHO growth reference median, respectively.

Waist circumference (WC) will be measured to the nearest 0.1 mm using Gulick anthropometric tape between the lower border of rib margin and the upper border of iliac crest (WC-mid).

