3.10. Statistical analysis

The analyses will be performed in the PQStat v1.8.0 program and the Statistica software version 12 (StatSoft. Inc. 2014, Tulsa, USA) with significance taken as $p < 0.05$. Descriptive statistics of groups will be presented as mean and standard deviation, median and quartiles, as well as numbers and percentages, depending on the data type. The normal distribution of the data will be verified using the Shapiro–Wilk test, and the comparison of the variance of variables between the groups will be performed using the Fisher–Snedecor test. Quantitative data describing two independent groups and meeting the normal distribution will be compared using the Student’s t-test or the Student’s t-test with the Cochran–Cox correction, when the variances of the groups being compared are significantly different. The Mann–Whitney test will be used when the assumption of normal distribution is not met. The dichotomous data will be compared with the chi-square test or the Fisher’s exact test when the Cochran conditions for using the chi-square test is not met. For the ordered category data, the Cochran–Armitage trend test will be used. Pearson correlation coefficient (for normally distributed variables) and Spearman’s rank correlation (when the assumption of normality is not met) will be calculated to evaluate association between two quantitative variables.

Logistic regression (univariate and multivariate) will be carried out to identify the independent predictors of dichotomous outcomes. A multiple linear regression analysis model will be built to explain the selected dependent quantitative variables.

5. Selected literature references:

2. The Rotterdam ESHRE/ASRM-Sponsored PCOS Consensus Workshop Group. Revised 2003 consensus on diagnostic criteria and long-term health risks related to polycystic ovary syndrome (PCOS) The Rotterdam ESHRE/ASRM-sponsored PCOS consensus workshop group. *Hum. Reprod.* 2004, 19, 41–47, doi:1093/humrep/deh098.
3. World Health Organization. Growth Reference 5-19. BMI-for-Age for Girls. 2007. Available online: https://www.who.int/growthref/bmifa_girls_5_19years_z.pdf?ua=1 (accessed on 21 July 2020).

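### Does the protocol tie the overweight/obesity analysis to a yes/no EAT-26 cut at 20, and lose power by it?

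*Protocol*

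**What the plan says.** Section 1 sets, as one objective, to identify "factors that increase the risk of being overweight and of obesity among adolescents with clinical features of PCOS, related to diet and DEA". Section 2 gives the size: "The research will be carried out with the participation of 200 Caucasian adolescent girls". Section 3.1.1 defines the outcome: "overweight and obesity correspond to BMI-for-age greater than 1 standard deviation", with a second limit at 2 standard deviations for obesity.

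Section 3.7 describes the EAT-26: 26 items worth 0 to 3 points each, so a total of 0 to 26 × 3 = 78. It ends with the category: "A total score of 20 or more points indicates DEA (Disordered Eating Attitudes".

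Section 3.10 assigns methods by type of data and not by variable:
- "Quantitative data describing two independent groups and meeting the normal distribution will be compared" by t-test, or by Mann–Whitney where normality fails.
- Pearson or Spearman coefficients "will be calculated to evaluate association between two quantitative variables".
- "For the ordered category data, the Cochran–Armitage trend test will be used".
- Logistic regression, univariate and multivariate, "will be carried out to identify the independent predictors of dichotomous outcomes".

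No outcome, predictor or coding is named for any regression.

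**The concern.** The objective names DEA, DEA is defined by a threshold, and overweight/obesity is an outcome suited to logistic regression. Put together, these suggest a model with DEA as a yes/no term, in which totals of 2 and 19 count the same. Splitting a score that can run from 0 to 78 at one point discards information. If the relation is graded, a study of 200 could miss a modest association and report that disordered eating is unrelated to weight. If the analysts chose between the numeric and yes/no forms after seeing results, the false-positive rate would exceed the nominal 5%.

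**Working it through.** **Inputs.** From the protocol: n = 200, significance at p < 0.05 (two-sided assumed), DEA at a total of 20 or more. The protocol gives no power calculation, so there is no figure to reproduce. Assumed: DEA in 10–30%, overweight/obesity in 30–50%, a right-skewed integer score (gamma, shape 1.3), one predictor in the model, logistic likelihood-ratio test, 3,000 simulated studies per scenario.

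**1. Power if the relation is graded (r = 0.20)**
- DEA yes/no in logistic regression: 26–41%.
- Raw score in logistic regression: 50–57%; square root of the score: 56–63%.
- Mann–Whitney comparison of the score between weight groups: 55–60%.

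Hand check of the cut, with DEA 20% and overweight 40%. The implied risks are 51.1% with DEA (40 girls) and 37.2% without (160 girls), an odds ratio of (0.511/0.489)/(0.372/0.628) = 1.76.
- Difference: 0.511 − 0.372 = 0.139.
- Standard error under no difference: √[0.40 × 0.60 × (1/40 + 1/160)] = 0.0866.
- Standard error under the difference: √[0.511 × 0.489/40 + 0.372 × 0.628/160] = 0.0878.
- Power ≈ Φ[(0.139 − 1.96 × 0.0866)/0.0878] = Φ(−0.35) = 36%, inside the simulated range.

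A second simulation, with the effect set as an odds ratio of 1.5 per standard deviation and both normal and skewed scores, points the same way: 72–81% for the numeric score and 35–58% for the cut.

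**2. Power if risk steps up at 20**
- Odds ratio 3: cut 60–94%, raw score 36–81%, square root 27–80%.
- Odds ratio 2: cut 29–60%, raw score 19–44%, square root 14–42%.

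Hand check, odds ratio 3, DEA 15%, overweight 40%. Solving 0.85·p₀ + 0.15·3p₀/(1 + 2p₀) = 0.40 gives p₀ = 0.36 and p₁ = 0.628, in groups of 170 and 30.
- Difference: 0.268.
- Standard errors: √[0.24 × (1/30 + 1/170)] = 0.0970 under no difference; √[0.628 × 0.372/30 + 0.36 × 0.64/170] = 0.0956 under the difference.
- Power ≈ Φ[(0.268 − 1.96 × 0.0970)/0.0956] = Φ(0.81) = 79%. The raw score reaches 60% in the same scenario.

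So the better form depends on the shape of the relation, on which the protocol is silent.

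**3. How firm the gain is.** The graded figures in step 1 are reproduced when the tendency to overweight is linear in the normal-transformed score. With linearity in the raw score, the cut reaches 38–45%, the raw score 60–64% and the square root 57–60%. The direction stays, the gap narrows, and the square root no longer leads.

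**4. What the text fixes.** Section 3.7 is one of several measurement sections (3.1 to 3.9), none of which assigns its variable to a test. Section 3.10 does that, by data type. The EAT-26 total is a quantitative variable and falls under the quantitative rules as every other unnamed quantitative measure does. By step 1, the Mann–Whitney test those rules allow has about the same power as the numeric score in a one-predictor logistic model. That DEA enters the regression as yes/no is an inference from the two sections and is not stated in either.

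**5. False positives.** With no relation, each test alone rejects in 4–6% of studies; counting either the cut or the square-root score as a finding gives 8–9%. That inflation requires both forms to be tested for the same claim. The protocol announces no such pair of tests.

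**The case for a change.** The strongest contrary case is that DEA, as defined, is the exposure named in the objective; that the cut is the only use of the total the protocol spells out; and that only a multivariable model speaks to independent prediction. The two-group tests and correlations are unadjusted and do not replace it, and a trend test across normal, overweight and obese girls would still take DEA as yes/no (32–47% power at r = 0.20). Naming the numeric score would need no new data.

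Much of this stands. The yes/no reading is natural, the loss under a graded relation is real, and settling the form of the predictor beforehand is good practice.

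It does not amount to a fault in the protocol. The same argument also works for the cut: the stated factor is DEA, and a yes/no DEA term answers the question in the investigators' own terms. Making the score principal would replace that exposure with a related one, on a belief about shape that the protocol neither states nor supports. Checking the shape in the data would settle little: adding the DEA indicator to the square-root score detects a step of odds ratio 2.5 in only 29–42% of studies.

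**Conclusion.** The concern does not hold. The protocol defines DEA by a conventional-looking category and leaves the coding of every regression predictor open; it neither requires the yes/no form nor rules out the numeric score. That choice commonly belongs to a statistical analysis plan, so its absence here is not a finding.

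The power difference is conditional. Under a modest graded relation the numeric score leads (50–63% and 26–41%); under a step at 20 with odds ratio 3 the cut leads (60–94% and 36–81% for the raw score). All these figures rest on assumed shares of DEA and overweight, an assumed score shape and effect, and a single predictor; only n = 200, the 5% level and the cut at 20 come from the protocol. The multivariate models that section 3.10 also plans were not simulated.

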3.8. The Data From The Child’s Health Book

The data were collected from the child’s health book regarding newborn body weight and term of delivery. The incidence of macrosomia (body weight over 4000 g) or low birth weight, LBW (body weight less than 2500 g) was assessed on the basis of the newborn’s body weight. The full term of

delivery (term births) will be assessed for deliveries that occur between 38–42 weeks of pregnancy, while preterm births will be defined as those deliveries between 23 weeks and 37 weeks.

3.9. Evaluation of physical activity

For this purpose the International Physical Activity Questionnaire will be applied, including records of the type and specific character of the training and activity, its duration, intensity and frequency.

3.10. Statistical analysis

The analyses will be performed in the PQStat v1.8.0 program and the Statistica software version 12 (StatSoft. Inc. 2014, Tulsa, USA) with significance taken as $p < 0.05$. Descriptive statistics of groups will be presented as mean and standard deviation, median and quartiles, as well as numbers and percentages, depending on the data type. The normal distribution of the data will be verified using the Shapiro–Wilk test, and the comparison of the variance of variables between the groups will be performed using the Fisher–Snedecor test. Quantitative data describing two independent groups and meeting the normal distribution will be compared using the Student’s t-test or the Student’s t-test with the Cochran–Cox correction, when the variances of the groups being compared are significantly different. The Mann–Whitney test will be used when the assumption of normal distribution is not met. The dichotomous data will be compared with the chi-square test or the Fisher’s exact test when the Cochran conditions for using the chi-square test is not met. For the ordered category data, the Cochran–Armitage trend test will be used. Pearson correlation coefficient (for normally distributed variables) and Spearman’s rank correlation (when the assumption of normality is not met) will be calculated to evaluate association between two quantitative variables.

Logistic regression (univariate and multivariate) will be carried out to identify the independent predictors of dichotomous outcomes. A multiple linear regression analysis model will be built to explain the selected dependent quantitative variables.

5. Selected literature references:

2. The Rotterdam ESHRE/ASRM-Sponsored PCOS Consensus Workshop Group. Revised 2003 consensus on diagnostic criteria and long-term health risks related to polycystic ovary syndrome (PCOS) The Rotterdam ESHRE/ASRM-sponsored PCOS consensus workshop group. *Hum. Reprod.* 2004, 19, 41–47, doi:1093/humrep/deh098.
3. World Health Organization. Growth Reference 5-19. BMI-for-Age for Girls. 2007. Available online: https://www.who.int/growthref/bmifa_girls_5_19years_z.pdf?ua=1 (accessed on 21 July 2020).

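### The variance pre-test in section 3.10 lets two-group t-tests drift from 5% when the BMI groups are clearly unequal in size and moderately unequal in spread (minor, one-sentence fix)

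*Protocol*

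**What the plan says.** Protocol section 3.10 takes significance as p < 0.05 for all analyses. It checks normality with Shapiro–Wilk and states that "the comparison of the variance of variables between the groups will be performed using the Fisher–Snedecor test". For "Quantitative data describing two independent groups and meeting the normal distribution", it uses the ordinary Student t-test, or the Cochran–Cox version "when the variances of the groups being compared are significantly different". Data that fail the normality check go to Mann–Whitney. The F-test is given no level of its own.

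Section 3.10 does not name the groups. The two-group contrast that the objectives suggest is in section 1, which looks at markers and nutrient intake "in normal and overweight/obese girls with clinical features of PCOS". Section 3.1.1 defines the groups by measurement: "overweight and obesity correspond to BMI-for-age greater than 1 standard deviation" (2 for obesity). Section 2 plans 200 girls in total. No group sizes, SDs or expected differences are given.

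**The concern.** The rule treats a non-significant F-test as evidence that the variances are equal. It is only a failure to detect a difference, and with a small second group that failure is common. The pooled t-test is then applied where its assumption is false. With equal group sizes this does little harm. With unequal sizes the pooled standard error is too small when the smaller group is the more variable, and too large when it is the less variable.

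BMI category is observed and not allocated, so the plan has no control over the split. At stake is whether the p-values for normally distributed measures mean what section 3.10 says they mean. The error can go either way: slightly too many false positives, or slightly too little power.

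**Working it through.** **Inputs from the protocol.** Nominal level 0.05, F-test gate, and Student or Cochran–Cox branch (section 3.10); N = 200 (section 2).

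**Assumed, because the protocol is silent.** Two-sided tests, F-test at 0.05, splits from 100/100 to 180/20, and SD ratios (smaller group to larger group) from 0.5 to 2.

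**Reference point.** The only figure on this point is the 5% level. Simulating the rule with equal SDs gives 4.98% at 100/100 and 5.07% at 150/50, so the simulation recovers the nominal level when the pooled assumption holds.

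**Why the pooled test errs.** Take 140/60 with SDs 1 and 1.2.

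- Expected pooled variance: (139 × 1 + 59 × 1.44) / 198 = 223.96 / 198 = 1.131.
- Variance the pooled test assumes for the mean difference: 1.131 × (1/140 + 1/60) = 1.131 × 0.02381 = 0.02693.
- True variance: 1/140 + 1.44/60 = 0.00714 + 0.02400 = 0.03114.
- Ratio of standard errors: √(0.02693 / 0.03114) = 0.930.
- Effective critical value: 1.972 × 0.930 = 1.834, a two-sided normal tail of about 6.7% instead of 5%.

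**Why the gate does not repair this.** In the same setting the F-test is significant in 40% of samples. The other 60% go to the pooled test, which rejects 7.0% of the time there and contributes 0.60 × 7.0% = 4.2 points. The overall rate is about 5.7%, so the Cochran–Cox branch contributes 5.7 − 4.2 = 1.5 points.

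**The whole rule, simulated.** Normal data, equal means, Cochran–Cox (weighted critical value) in the second branch. Separate runs used 100,000 to 2,000,000 replicates per setting, and a range is shown where they differ. At 200,000 replicates the simulation standard error is √(0.05 × 0.95 / 200,000) = 0.05 points.

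| Split | F-test significant at SD ratio 1.2 | Type I error, ratio 1.2 | Type I error, ratio 0.83 |
|---|---|---|---|
| 100/100 | 44% | 4.8–4.9% | 5.0% |
| 120/80 | 43% | 5.3% | 4.6–4.7% |
| 140/60 | 40% | 5.6–5.8% | 4.4% |
| 150/50 | 37% | 6.0% | 4.2% |
| 160/40 | 33% | 6.3–6.4% | 4.0% |
| 170/30 | 28% | 6.8–6.9% | 3.7–3.8% |

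**Across SD ratios at 150/50.** 5.7% at 1.1, 6.0% at 1.2, 5.9% at 1.25, 5.4% at 1.4, 5.1% at 1.5 and 4.9% at 2.0. The excess peaks at a modest ratio and disappears once the F-test almost always detects the difference.

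**Without the gate.** The Welch test gives 4.9–5.1% at every setting in the table. Cochran–Cox used throughout gives 4.7–5.0% across the settings with N = 200. Putting Welch in the second branch of the gated rule changes its error by less than 0.1 point, so the result does not depend on how that branch is computed.

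**Adding the normality gate.** With Shapiro–Wilk and Mann–Whitney included (20,000 replicates, normal data, Welch branch) the rates are 5.8% at 140/60 and 6.8% at 160/40 for ratio 1.2, and 7.0% at 170/30 for ratio 1.3. The departure therefore remains for variables that are truly normal.

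**The case against.** The strongest reply is that the effect is too small and too conditional to matter. Much of that stands.

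- **Size.** At 120/80 the excess is about 0.3 points, and with equal groups there is none.
- **The gate does useful work.** At 140/60 and SD ratio 2, ungated Student would reject 12.6% of the time, while the protocol's rule rejects about 5%.
- **Reach.** A reader might infer that dozens of hormones, cytokines, nutrients and dental indices are affected. Section 3.10 sends non-normal variables to Mann–Whitney first. Under an assumed lognormal shape at 140/60, both groups pass Shapiro–Wilk in only 17% of samples at a coefficient of variation of 20%, and in 1% at 31%. Skewed markers would seldom reach the t-test.
- **Groups.** A reader might also extend the point to girls with and without disordered eating attitudes, or to birth-weight groups, where splits could be extreme. The protocol records these as dichotomous characteristics and nowhere says that means are compared between them.
- **Conditional rates.** Among comparisons left to the pooled test, rejection can exceed 12% (170/30, ratio 1.4). That is not the error rate of the procedure; the overall rate there is about 6.4%.
- **Purpose.** The protocol names no primary endpoint or confirmatory test, so a shift of a fraction of a point is unlikely to overturn a conclusion.

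What does not stand is the idea that the rule is as good as the alternative. It is written into the protocol rather than left to a later plan, and a better-calibrated test is available at almost no cost.

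**Conclusion.** The point holds as a minor one. For two-group comparisons of normally distributed measures, the F-gated rule does not hold the stated 5% when group sizes are clearly unequal and the SD ratio is roughly 1.1 to 1.5. The excess is about 0.3 to 1.4 points from 120/80 to 160/40 and about 1.8 points at 170/30 (ratio 1.2, smaller group more variable). In the opposite direction the rule is conservative by a similar order.

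It would be wrong to read this as a failure whenever sizes and spreads differ. Near an SD ratio of 2 the rule is back at about 5%, and equal sizes remove the problem. The mechanism is certain, but its size in this study is unknown: every split and SD ratio here is assumed, the two-sided tests and the 0.05 level for the F-test are assumed, and the BMI contrast is taken from the objectives because section 3.10 names no groups.

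**What to change.** In section 3.10, remove the Fisher–Snedecor test as the means of choosing the t-test, and state that two-group comparisons of means always use the unequal-variance (Welch) t-test. Using the already named Cochran–Cox version throughout would also hold the level, slightly on the conservative side.

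The change is one sentence and needs no new data. The cost is some power when the variances really are equal. From a starting power of about 80%, Welch loses less than half a point at 140/60, about 0.9 points at 160/40 and about 1.6 points at 170/30.
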